9.6.2 Physical Examinations/Limited Physical Assessments

The results of physical examinations will be collected as adverse events if clinically significant or as medical history (if observations are noted prior to TGFR start). Physical exam data will not be listed.

9.6.3 Clinical Laboratory Assessments

Clinical laboratory tests include clinical chemistry, hematology, urinalysis and coagulation parameters. Each parameter will be summarized using the descriptive statistics. Details will be specified in the Statistical Analysis Plan (SAP). Also, individual subject results will be assessed against an appropriate reference range if available. The manifestation of any clinically significant abnormality that develops during the study will be reported as an AE.

9.6.4 ECGs

ECG data will be listed. Clinically significant findings noted after dosing will be noted as adverse events.

9.6.5 **Prior and Concomitant Therapies**

Concomitant medications administered within 3 days prior to MB-102 dose administration and through the follow-up study visit will be listed. Medications will be coded using the World Health Organization (WHO) drug dictionary. Data will be provided in one or more subject data listings. Concomitant non-drug therapies will be listed.

9.7 Determination of Sample Size

For a P30 true value of 0.95, alpha of 0.025, performance goal of 85%, power of 90%, the one-sided exact binomial test yields a sample size of 102.

9.8 Missing Data

Missing values will not be imputed.

10 Quality Assurance and Quality Control

10.1 Training

The clinical site will be trained on the protocol and study procedures. In addition, Sponsor representatives may be onsite during dosing procedures for the initial subjects at each site to assist sites with the operation of the MediBeacon[®] Transdermal GFR Measurement System.

10.2 Audit and Inspection

The study site and study documentation may be subject to quality assurance audits during the course of the study by the sponsor, or its nominated representative. In addition, inspections may be conducted by regulatory authorities at their discretion.

10.3 Monitoring

Data for each subject will be recorded in an electronic data capture (EDC) system. Data collection must be completed for each subject enrolled in the study.

In accordance with GCP and International Council on Harmonization (ICH) guidelines, the study monitor will conduct monitoring visits at regular intervals. During the visits, the study monitor will perform the source document verification and verification that investigator's obligations and all applicable regulatory requirements are being fulfilled. The frequency of monitoring visits will be determined by the rate of subject recruitment.

The investigator must permit the monitor, the IEC, the sponsor's internal auditors and representatives from regulatory authorities direct access to all study-related documents and pertinent hospital or medical records, including direct access to electronic medical records for confirmation of data contained within the EDC system. Subject confidentiality will be protected at all times.

10.4 Data Management and Coding

MediBeacon or designee will be responsible for activities associated with the data management of this study. This will include setting up a relevant database and data transfer mechanisms, along with appropriate validation of data and resolution of queries. Data generated within this clinical study will be handled according to the relevant SOPs at MediBeacon or their designee.

Study sites will enter data into a 21 CFR Part 11 compliant electronic data capture (EDC) system via a secure internet connection. Data entered into the EDC system must be verifiable against source documents at the study site. Any changes to the data entered into EDC system will be recorded in the audit trail.

Missing or inconsistent data will be queried via the EDC system to the investigator for clarification. Subsequent modifications to the database will be documented.

Fluorescent data from the TGFR System will be downloaded to hard media then transferred electronically to the Data Management designee via a secure data transfer process per the Study Procedure Manual.

All medical terms (medical history, concomitant medications and adverse events) will be coded.

10.5 Protocol Deviations

The Investigator will not deviate from the clinical protocol without the prior written approval of MediBeacon except in medical emergencies or in unforeseen, isolated instances where minor changes are made that will not increase the subject's risk or affect the validity of the study. In medical emergencies, prior written approval for protocol deviations will not be required, but MediBeacon or their designee must be notified via telephone within 24 hours of occurrence. Prospective approval of protocol deviations to recruitment and enrolment criteria (also known as protocol waivers or exemptions) are not permitted.

Major Protocol Deviation is a significant deviation from the protocol that may impact subject safety and/or affect the integrity of clinical trial data. These may include, but are not limited to the following:

- Improper or inadequate informed consent procedures
- Subject did not meet eligibility criteria
- Subject received prohibited concomitant medication(s) at any time during the trial
- A significant protocol required assessment or procedure was not performed per protocol requirements

- Subject received incorrect study medications at any time during the trial
- Significant departure from protocol-required dosing (dosing extravasation)
- Subject developed criteria that required withdrawal from study protocol but was not withdrawn
- The sensor was removed prior to measurement of a tGFR
- An Average Session GFR or an Average Snapshot GFR was not obtained
- Sensors that are not cleaned and disinfected between study subjects

A Minor Protocol Deviation is a deviation that does not impact subject safety and/or compromise the integrity of the clinical trial data.

Subjects who experience a sensor dislodgement, a dosing or device issue or an extravasation (which would be considered a major deviation) will have PK sample collection discontinued and the sensor removed, but will be asked to remain in the study for safety follow-up (including dosing day safety assessments and the follow-up visit). The event that triggered the discontinuation of PK / fluorescent data collection will be considered the protocol deviation, however missing PK sample collections will not need to be documented as individual protocol deviations.

Deviations will be documented at the site and submitted to the IEC (as required) and the sponsor.

10.6 Direct Data Collection

Fluorescent measurements will be collected directly by the MediBeacon[®] Transdermal GFR Measurement System and will not appear on any available source documentation with the exception of the tGFR which will be recorded onto the site source document and transcribed into the EDC. The MediBeacon[®] Transdermal GFR Measurement System will be a closed system.

11 Records / Retention

Essential documents are those documents that individually and collectively permit evaluation of the study and quality of the data produced. After completion of the study, all documents and data relating to the study will be kept in an orderly manner by the investigator in a secure study file. All study records will be available for inspection by the sponsor or its representatives, or a regulatory agency.

Investigator files containing all records and reports of the investigation should be retained for a minimum of two (2) years (US) after the completion/ termination of the investigational study or the date that the records are no longer required for purposed of supporting a premarket approval application. The Sponsor will determine with the investigational site as to this exact date so that the minimum two-year record retention can be accomplished. Records may be discarded upon written notification by the Sponsor. To avoid error, the Principal Investigator should contact MediBeacon, before the destruction of any records and reports pertaining to the study to ensure they no longer need to be retained.

In addition, in accordance with the Clinical Trial Agreement, the Sponsor should be contacted if

the Principal Investigator plans to leave the investigational site so that appropriate arrangements for file custodianship can be made.

The following records must be maintained in designated study administrative files:

- Clinical protocol and all amendments
- Signed Investigator Agreement
- Independent Ethics Committee Approval Letter(s)documenting review and approval of all protocols, amendments, IBs, ICFs, subject materials, etc.
- IEC-approved informed consent(s) (including any revisions)
- Current CV for all Investigators and subinvestigators including evidence of current medical licensure
- Financial Disclosure Form for all Investigators
- Site Delegation of Authority Log
- Correspondence relating to this study
- Correspondence with the IEC
- IEC membership list and/or assurance
- Investigational site authorized study personnel signature list and delegation of authority
- Device Instructions for Use
- Lab certification, including a set of the lab's normal range for tests performed
- EDC Completion Guidelines
- Subject Screening & Enrolment Log
- Site Visit Log (e.g. for Monitor sign-in)
- Site Training records
- Investigational Device and Drug Accountability Logs
- Reports (includes Adverse Event reports and final reports from Investigator and Sponsor)
- Copy of all EC approved subject-related materials and/or study advertising materials

The following records must be maintained for each subject enrolled in the study:

- Signed subject consent forms
- Electronic copy of final completed case reports (to be provided by the sponsor at the end of the study)
- Jump drive with subject's fluorescent data from the TGFR system
- All lab work and testing results
- Record of any complications, adverse events, device problems and/or malfunctions, with supporting documentation
- Procedure reports, progress notes, physician and/or nursing notes, and subject office files
- Records pertaining to subject deaths

12 Ethics

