Study Design:	 Multi-center, bridging, adaptive open-label pharmacokinetic study comparing transdermal measured GFR (tGFR) to plasma-derived indexed GFR (nGFR). As the reusable sensor is new, an adaptive trial design will be employed. Run-in cohort of up to 30 evaluable subjects will commence the study. Additional Run-in subjects may be enrolled at new clinical sites to ensure protocol compliance. Run-in subject data will be considered tuning data. Validation Cohort 1 (approximately 20 evaluable subjects) will be used to confirm final algorithm selection. Validation Cohort 1 subject data will be considered tuning data. Validation Cohort 2 (approximately 75 evaluable subjects) will be analyzed in an interim analysis to compare results against the primary endpoint specification. If the primary endpoint has been achieved, the study will be terminated. If not, the trial will be continued. Validation Cohort 3 (approximately 65 evaluable subjects) will be enrolled in the event the interim analysis did not meet the primary outcome measure. Final analysis will be of the 140 evaluable subjects. 				
Number of Treated Subjects:	 Up to 240 subjects are planned for enrollment. The population will be split into stratums in accordance with screening eGFR measured by the CKD-EPI equation (pre-2021): Stratum 1: 50% of evaluable subjects with an eGFR ≥ 70 mL/min/1.73 m² Stratum 2: 50% of evaluable subjects with an eGFR < 70 mL/min/1.73 m² 				
	skin scale (FSS) I-III and 50% of subjects will have FSS IV-VI. Subjects will be				

	enrolled across a spectrum of both eGFR ($<120 - >15$ mL/min/1.73 m ²) and FS					
	An adaptive trial design will be employed. A Run-in cohort of 30 evaluable subjects and Validation Cohort 1 of up to 20 evaluable subjects with a mixture of eGFR and FSS will enroll to provide tuning data and allow algorithm finalization. This will be followed by up to 140 additional evaluable subjects enrolled: after 75 evaluable subjects in Validation 2 Cohort have been completed, an interim analysis will be conducted to compare results against the primary endpoint specification. If the primary endpoint has been achieved, the study will be terminated. If not, the trial will be continued with Validation Cohort 3 until 140 evaluable subjects are enrolled. Subjects with incomplete assessments or major protocol deviations may be					

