6.7.1 Stratum 1 (12 hour follow-up)

During the course of the study day, it is particularly important for site teams to check the patency of PK catheters. If a catheter is determined to be compromised in anyway, another catheter may be placed in the same arm as the original catheter utilizing a different vein. Direct sticks may also be used to obtain blood.

PK draws will be drawn via the venous catheter at the following timepoints:

- PK draw in K₂ EDTA tube at 5 minutes (± 2 minute)
- PK draw in K_2 EDTA tube at 15 minutes (±2 minute)

- PK draw in K₂ EDTA tube at 30 minutes (±2 minutes)
- PK draw in K_2 EDTA tube at 60 minutes (± 2 minutes)
- PK draw in K_2 EDTA tube at 90 minutes (±2 minute)
- Vital sign collection at 90 minutes (±5 minutes)
- PK draw in K_2 EDTA tube at 120 minutes (± 5 minutes)
- PK draw in K₂ EDTA tube at 180 minutes (±5 minutes)
- PK draw in K₂ EDTA tube at 240 minutes (±5 minutes)
- Vital sign collection at 250 minutes (±5 minutes)
- PK draw in K₂ EDTA tube at 300 minutes (±5 minutes)
- PK draw in K_2 EDTA tube at 360 minutes (± 5 minutes)
- PK draw in K₂ EDTA tube at 480 minutes (±5 minutes)
- Vital sign collection at 500 minutes (±5 minutes)
- PK draw in K_2 EDTA tube at 600 minutes (±5 minutes)
- Perform a 12 lead ECG at 700 minutes (±5 minutes)
- Vital sign collection (includes temperature) at 710 minutes (±5 minutes)
- PK draw in K_2 EDTA tube at 720 minutes (± 5 minutes)
- Obtain laboratory tests including chemistry, hematology, and urinalysis (See Section 7.1.2.6 and Table 3) at 725 minutes (-245 minutes)
- At the conclusion of TGFR measurements (when tGFR is reported on the monitor), the sensor may be removed
- Adverse events will be collected based on subject reports and medical team observations

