2.3 Replacement of Subjects

Should a subject not meet eligibility, or is unable to be scheduled for dosing, that subject will be considered a screen failure. In addition, subjects who are unable to have an "average session GFR" measured by the TGFR Measurement System (due to premature sensor removal, for example), a major protocol deviation (such as a dosing extravasation), or meet the agreed upon post-PK outlier exclusion criteria (defined in **Section 5.4**) may be replaced to ensure the minimum sample size is enrolled. If subjects are not considered evaluable, they will be replaced in the study with a total potential enrollment up to 240 subjects. All subjects with exposure to MB-102 will be included in the safety analysis.

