5.4 Treatment of Outliers in Pharmacokinetic Analysis

Four outlier exclusion criteria which will be identified following PK analysis are addressed below.

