5.4.3 Exclusion Based on Small Dosing Errors and/or Extravasations

MediBeacon have found that plasma determined nGFR may also be affected by more subtle issues. These include small dosing errors and/or small extravasations of the MB-102 dose.

For example, after deleting the two extreme outliers in **Figure 2**, and correcting for a small linear trend in the absolute difference between $nGFR_{BSA}$ and $nGFR_{Vd}$ for the remaining subjects, the root mean square (RMS) percent error of the difference of the two indices was computed in 20 mL/min wide $nGFR_{Vd}$ subject bins, as shown in the **Figure 3**:

Figure 3: RMS percent error of nGFR_{BSA} - nGFR_{Vd} as a function of nGFR_{Vd}.

Subjects were grouped into 20 mL/min wide bins according to $nGFR_{Vd}$. Error bars represent \pm the standard error within each binned group of subjects.

Statistical Analysis Plan		Page 20 of 29
MediBeacon Inc.	An Open Label, Multi-Center, Safety and Pharmacokinetic Bridging Study of MB-102 (Relmapirazin) and the Use of the MediBeacon [®] Transdermal GFR Measurement System using the TGFR Reusable Sensor with Disposable Adhesive Ring in Normal and Renal Compromised Subjects for the Evaluation of Kidney Function	Ver 4.0

The resulting RMS percent error is seen to be independent of $nGFR_{Vd}$ with a combined value of 13% across all subjects.

Choosing two times the RMS percent error as a threshold limit for outlier detection (since it is similar to the standard deviation) results in identification of four additional outlier subjects, as shown in the **Figure 4** below.

Figure 4: RMS percent error for $nGFR_{BSA}$ - $nGFR_{Vd}$ as a function of $nGFR_{Vd}$. Dashed lines are outlier thresholds

Summary: Two nGFR indexing calculations, $nGFR_{BSA}$ and $nGFR_{Vd}$, will be performed for all subjects in the 100-201 study. Any subject nGFR data that is an obvious outlier as described in section 2 above, and

Statistical Analysis Plan		Page 21 of 29
MediBeacon Inc.	An Open Label, Multi-Center, Safety and Pharmacokinetic Bridging Study of MB-102 (Relmapirazin) and the Use of the MediBeacon [®] Transdermal GFR Measurement System using the TGFR Reusable Sensor with Disposable Adhesive Ring in Normal and Renal Compromised Subjects for the Evaluation of Kidney Function	Ver 4.0

any subject nGFR that is outside the threshold boundary as described in **Figure 4** will be eliminated before applying the remaining nGFR data to the evaluation of the tGFR endpoint criteria.

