8.1 Analysis Sets

The following analysis populations will be defined for the study:

- Intent-to-Measure (ITM) Population The ITM population will consist of all subjects who are enrolled in the study in Stratum 1 & 2 and for whom an average session tGFR or an average snapshot tGFR* has been calculated, and who have not had any major protocol deviations that would impact TGFR system performance.
- Modified Intent-to-Measure (mITM) Population The mITM population will consist of all subjects in the ITM population with no outlier PK parameters.
- Safety Population The safety population will consist of all subjects who are enrolled in the study and have been dosed with MB-102.
- Pharmacokinetic (PK) Population The pharmacokinetic population will consist of all subjects who are enrolled in the study and have any PK data.

* Note: this includes short gaps in data that are less than 30 minutes due to a resumption of the monitoring session where an "average snapshot GFR" is reported instead of an "average session GFR".

The mITM population will be the primary analysis set for all effectiveness analyses. The Safety Population will be used for the analysis of all safety variables and baseline characteristics. The PK Population will be used for the analyses of PK data.

The ITM and mITM populations will be analyzed from subjects enrolled in the Validation 2 and Validation 3 (if applicable) cohorts only.

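### Two judgement-based exclusions from the primary set can be made with the device result in view; mask the people who decide and sign the evaluability list before each look

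*Protocol*

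**What the plan says.** **The device result comes first.** The study is open-label. Protocol 6.7.1 and 6.8 allow the sensor to come off once the monitor reports a tGFR. Protocol 10.6 says fluorescence measurements do not appear on source documents, "with the exception of the tGFR which will be recorded onto the site source document and transcribed into the EDC". The same section calls the device a closed system, but the exception means that this does not hide tGFR. Protocol 10.4 adds that the sponsor "or designee will be responsible for activities associated with the data management of this study". No access restriction on the tGFR field is described.

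**Exclusions come later.** SAP 5.4 opens: "Four outlier exclusion criteria which will be identified following PK analysis are addressed below". The routes out of the primary set are:

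- *Deviations (SAP 8.1, Protocol 9.2).* The ITM set keeps only subjects "who have not had any major protocol deviations that would impact TGFR system performance". Protocol 10.5 gives an expressly non-exhaustive list of major deviations. Neither document says which of them affect performance, who decides, or when.
- *Obvious outliers (SAP 5.4.2, applied in the 5.4.3 summary).* The rule starts "Any subject nGFR data that is an obvious outlier as described in section 2 above, and" and gives no numeric limit for this first part. The sentence goes on to the numeric threshold, and says that both kinds are removed before the remaining nGFR data are used to evaluate the tGFR endpoint.
- *Numeric cuts (SAP 5.4.3 and 5.4.4).* These are twice the RMS percent error, and nGFR indexed to body surface area above 120. They are not at issue here.

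**Replacement and control.** SAP 2.3 states: "If subjects are not considered evaluable, they will be replaced in the study with a total potential enrollment up to 240 subjects". The mITM set, after all exclusions, is primary. SAP 8.2 states that overall type I error is controlled at one-sided 0.025. The only committee named is the Safety Review Committee, whose remit is safety.

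**The concern.** P30 counts subjects whose two GFR values agree. Someone who holds both values when judging evaluability can see which subjects are misses. A miss then invites a search for a reason to exclude, and an agreement does not. If misses leave the set more readily than agreements and new subjects take their places, the observed P30 sits above the true one. The 0.025 error rate in SAP 8.2 then no longer applies, because it presumes that exclusion is unrelated to agreement.

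The pass marks allow few misses, so a small number of one-sided decisions can matter.

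**Working it through.** **1. The plan's own figure.** Inputs from Protocol 9.7 and SAP 8.2: performance goal 0.85, true P30 0.95, one-sided alpha 0.025, power 0.90, exact binomial test. At n = 102 the smallest passing count is 94: P(X ≥ 94 | 0.85) = 0.0231, with power 0.930 at 0.95. Power stays at or above 90% for every larger n checked (to 159). The stated 102 is reproduced.

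**2. Pass marks at the two looks** (one-sided nominal 0.0150 at 75 and 140 subjects, SAP 8.2):

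| Result | Exact p at 0.85 | Outcome |
|---|---|---|
| 70/75 | 0.0234 | continue to Cohort 3 |
| 71/75 | 0.0084 | success, stop |
| 128/140 | 0.0170 | fail |
| 129/140 | 0.0083 | success |

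The limits are therefore 4 misses in 75 and 11 in 140.

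**3. Error rate with neutral exclusions.** Let S(p) = P(X₁ ≥ 71) + Σ P(X₁ = a)·P(X₂ ≥ 129 − a), summed over a ≤ 70, with X₁ ~ Bin(75, p) and X₂ ~ Bin(65, p). Then S(0.85) = 0.0145 and S(0.95) = 0.956. The boundaries are sound as long as exclusion is unrelated to agreement.

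**4. One-sided removal.** Suppose each miss is removed and replaced with probability q, and no agreement is ever removed. The effective P30 at a true 0.85 is p(q) = 0.85 / [0.85 + 0.15(1 − q)].

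| q | p(q) | Overall type I error S(p(q)) |
|---|---|---|
| 0 | 0.850 | 0.0145 |
| 5% | 0.856 | 0.0225 |
| 6% | 0.858 | 0.0245 |
| 7% | 0.859 | 0.0267 |
| 10% | 0.863 | 0.035 |
| 20% | 0.876 | 0.080 |

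The stated 0.025 is passed just above 6%. At a true P30 of 0.85, 140 subjects give 0.15 × 140 = 21 expected misses, and 6% of 21 is about 1.3 subjects. The values of q are assumptions; the documents give none.

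**5. A single subject at the interim.** At 70/75, one miss reclassified as unevaluable and replaced by an agreement gives 71/75, and p goes from 0.0234 to 0.0084. Without the change the trial continues and needs 129 − 70 = 59 of the next 65. The probability of that is 0.957 at a P30 of 0.95 and 0.126 at 0.85.

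**6. Room for replacement.** The 240 cap leaves 240 − 30 − 20 − 140 = 50 places, fewer if extra run-in subjects are enrolled. At q = 6% only 140 / 0.991 = 141.3 subjects would be needed on average. The cap is no brake.

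**7. How often the visual call arose.** In the earlier data in SAP 5.4.2, 2 of 67 subjects were called obvious outliers. At that rate, 2/67 × 75 = 2.2 and 2/67 × 140 = 4.2 subjects. The SAP expects the rule to be used seldom.

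**The case against.** Several stronger readings are tempting, and the documents do not support them.

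- *That nothing orders exclusion before comparison.* The SAP 5.4.3 summary does place removal of PK outliers before the endpoint evaluation, and the plot compares two plasma indices without using tGFR. An extreme point on it would normally breach the numeric limit as well. This leaves little discretion in the outlier call. What is missing is a mask, a named decision maker and a signed list. For deviations, SAP 8.1 gives no sequence at all.
- *That every deviation is open to selection.* Extravasation ends PK and fluorescence collection (Protocol 6.6), and so does sensor loss before a tGFR (7.1.2.5.1). Detachment from the monitor is graded by whether a tGFR is reported (5.5.2). In these cases there is normally no result to select on. What remains are deviations that leave a tGFR in place, such as eligibility failures, prohibited medication, an uncleaned sensor or a procedure not done as required (10.5), plus anything unlisted.
- *That sites can pick out misses.* A miss needs both values, and no text gives nGFR to sites. The exposure is in practice on the sponsor side, and even that is inferred from the EDC and data-management wording.
- *That one reclassified subject reverses the trial.* At 70/75 it changes the interim outcome only, since Cohort 3 follows.
- *That type I control is broken.* The exact design uses 0.0145 of the 0.025, so it absorbs removal of about 6% of misses.

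The planned ITM analysis also helps, because it restores PK outliers. It does not restore subjects excluded for deviations.

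**Conclusion.** The point stands as a cheap improvement that should be made. Two judgement-based exclusions, residual deviations and the obvious-outlier call, are open to anyone who holds both tGFR and nGFR. The deviation route is the wider of the two.

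The size is conditional. Overall type I error is 0.0145 with neutral exclusions and exceeds 0.025 once more than about 6% of misses, and no agreements, are removed and replaced. This assumes a true P30 of 0.85, independent subjects, and pass marks of 71/75 and 129/140. A reader might infer that selective removal took place, or that the error rate is already lost. The documents show neither. They show that the stated error control depends on a condition the plan does not secure.

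**What to change.** Amend SAP 5.4, 8.1 and 8.2, leaving the endpoint, boundaries and sample size as they are.

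1. Existing staff without access to tGFR values make the re-assay requests, the obvious-outlier call and the deviation-impact call, and the SAP names their role. They work from plasma, dosing and deviation data, and see only whether a tGFR was reported. The re-assay trigger in SAP 5.4.1 is already numeric (20% off the fit), so masking there is a precaution.
2. The evaluability list, with a reason for each exclusion, is signed and dated before tGFR and nGFR are merged. This is done at the 75-subject look and again for the remaining subjects.
3. Any later change to the list is reported with P30 both ways. P30 is also shown with deviation-excluded subjects who have both values added back, because the ITM analysis does not cover them.

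The cost is a SAP amendment, a restricted EDC view of the tGFR field, and a few days between PK completion and the P30 result at each look. Some role separation is also needed within existing staff. Protocol 10.1 allows sponsor representatives at dosing and 10.3 has monitors verify source, so those individuals should not be the ones who decide. No subjects or visits are added.
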